5.0 Investigational Plan

5.1 Overall Study Design and Plan: Description

This is an 88-week Phase 2b, randomized, double-blind, parallel-group, placebo-controlled multicenter study to evaluate the safety and efficacy of ABT-494 (upadacitinib) in adult subjects with moderate to severe AD.

The study was designed to enroll approximately 160 subjects to meet scientific and regulatory objectives without enrolling an undue number of subjects in alignment with ethical considerations. Therefore, if the target number of subjects has been enrolled, there is a possibility that additional subjects in screening will not be enrolled.

The duration of the study will be up to 88 weeks and will include a 35-day maximum screening period, a 16-week double-blind treatment period (Period 1) and a 72-week double-blind treatment period (Period 2). In addition, a 30-day follow-up visit (or phone call if a visit is not possible) should occur to determine the status of any ongoing AEs/SAEs or the occurrence of any new AEs/SAEs.

In Period 1, subjects will be randomized in a 1:1:1:1 ratio to one of four treatment groups: (1) ABT-494 7.5 mg, (2) ABT-494 15 mg, (3) ABT-494 30 mg, (4) matching placebo, once daily for 16 weeks. The primary endpoint analysis will be performed at Week 16. Randomization will be stratified by geographic region (US/PR/Canada, EU/AUS, and Japan). Enrollment in Japan will be capped at 10% of subjects (approximately 4 subjects per group).

Group 1: ABT-494 7.5 mg QD for 16 weeks

Group 2: ABT-494 15 mg QD for 16 weeks

Group 3: ABT-494 30 mg QD for 16 weeks

Group 4: Matching Placebo for 16 weeks

The analysis of the double-blind 16-week period of the study (Period 1), including the primary endpoint analysis, will be conducted after all subjects have either completed the

Period 1 or discontinued from the study; and the data regarding Period 1 have been cleaned and an interim database lock is performed. This efficacy analysis is the only and final analysis of the double-blind period, thus no adjustment of alpha-level is needed. In addition, there will be an interim analysis after all subjects have either reached Week 32 or discontinued from the study; and the data is cleaned.

In Period 1, discontinuation from study drug will be mandatory for any subject with an EASI score worsening of 25% or more compared with their Baseline EASI score at any 2 consecutive scheduled study visits from Week 4 to Week 12.

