 - d. Prior to other procedures; except for the questionnaires on the electronic hand-held device given to subjects to take home at Screening: daily Pruritus NRS, ADerm-SS and ADerm-IS Hand-held device usage stops at the Week 40 visit. Starting at the Week 52 visit, the questionnaires on the hand-held device (Pruritus NRS, ADerm-SS and ADerm-IS) will be given on the tablet during site visits. The MOS Sleep Scale questionnaire will stop at the Week 40 visit. The PGIS, POEM and DLQI questionnaires will be given on the tablet at site visits throughout the study.
 - e. Asthma Symptoms and Daytime Nasal Symptoms questionnaires are collected only for subjects with symptoms of asthma or rhinitis, respectively, at Screening and stop at the Week 40 visit.
 - f. Also note herpes zoster and hepatitis B vaccination status in medical history.
 - g. Collect SAEs and protocol-related nonserious AEs that occur after a subject signs the informed consent, prior to the first dose of study drug.
 - h. Refer to Section 5.3.1.1 Study Procedures TB Testing for specific requirements for TB testing and TB prophylaxis.
 - i. The screening chest x-ray will not be required if a subject had a previous normal chest-x-ray within 90 days of Screening, provided that all source documentation is available at the site.
 - j. For subjects with a normal ECG taken within 90 days of Screening, a repeat ECG at Screening will not be required, provided all source documentation is available.
 - k. Blood pressure, pulse rate, body temperature, and respiratory rate should be performed before blood draws are performed.

Table 2. Study Activities (Continued)

- l. A full physical exam is required at the visits indicated. A symptom-directed physical exam may be performed when necessary.
- m. For all females, collect serum for pregnancy test at screening and the Week 88 or PD visit. If serum pregnancy test comes back indeterminate or positive, a repeat test is necessary (pregnancy is an exclusion criterion); see Section 5.3.1.1 and Section 6.1.6 for details.
- n. Urine pregnancy test will be performed locally at every visit for all women of childbearing potential. If urine pregnancy test (which is performed at the site) is negative, begin or continue dosing. If urine pregnancy test is positive, withhold dosing and perform a serum pregnancy test. Pregnant subjects must discontinue from the study.

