- o. If time between visits is longer than 1 month, then collect the results of the monthly at home urine pregnancy test between scheduled visits (see Section 5.3.1.1). If a urine pregnancy test is positive, the subject must stop dosing, come in to the clinic and have blood drawn for a serum pregnancy test that will be analyzed at the central laboratory. A pregnant or breastfeeding female will not be eligible for participation or continuation in this study. The monthly at home tests between scheduled on-site visits are to occur at Weeks 28 and 36; unless an on-site visit is necessary due to rescue therapy with topical corticosteroids per Section 5.2.3.4.
- p. hsCRP results will remain blinded to the Sponsor, Investigator, study site personnel, and subject for all visits except Screening. Investigators should refrain from locally and periodically testing hsCRP and serum amyloid A. Investigators should also refrain from locally testing procalcitonin except for safety evaluations of signs and symptoms of infection or adverse events.
- q. Minimum 8-hour fast. If a subject is not able to fast when necessary, due to unforeseen circumstances, the non-fasting status will be recorded in study source documentation.
- r. A urine dipstick macroscopic urinalysis will be completed by the central laboratory at all required visits. A microscopic analysis will be performed in the event the dipstick results show leukocytes, nitrite, protein, ketones, or blood greater than negative or glucose greater than normal.
- s. For Japan only: for subjects with HBs Ab+ and/or HBc Ab+ at Screening, the HBV-DNA PCR test should be performed again at Week 12 and Week 24. In cases where the recurrence of HBV-DNA is observed, the subject should be discontinued from the study drug. Retesting at Week 12 and Week 24 is not necessary for subjects that have a history of HBV vaccine and are HBs Ab+.

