All subjects will be tested for the presence of HBV and HCV at Screening.

Hepatitis B:

Subjects will be tested for the presence of HBV at screening using the following tests:

HBs Ag

HBc Ab/anti-HBc

[figure not shown]
HBs Ab/anti-HBs (Hepatitis B surface antibody)

A positive result for HBs Ag will be exclusionary.

A negative result for HBs Ag will be tested (automatic reflex testing) for core antibodies (HBc Ab) and surface antibodies (HBs Ab).

- A negative test result for HBc Ab does **not** require HBV DNA PCR qualitative testing and the subject may be enrolled (Figure 2, Scenarios A and B). For a subject who has had a HBV vaccination (should document in the medical history), a positive test result for HBs Ab is expected and the subject may be enrolled (Figure 2, Scenario B).*
- A positive test result for HBc Ab requires HBV DNA PCR testing (automatic reflex testing) (Figure 2), (Scenarios C and D).
 - A positive result for HBV DNA or a result that exceeds detection sensitivity will be exclusionary.
 - A subject with a negative result for HBV DNA testing may be enrolled.
 - For Japan only: for subjects with HBs Ab+ and/or HBc Ab+ at Screening, the HBV-DNA PCR test should be performed again at Week 12 and Week 24. In cases where the recurrence of HBV-DNA is observed, the subject should be discontinued from the study drug. Retesting at Week 12 and Week 24 is not necessary with subjects that have a history of HBV vaccine and are HBs Ab+.

Figure 2. Criteria for HBV DNA PCR Qualitative Testing

* For subjects who have had a HBV vaccination (should document in the medical history), a positive test result for HBs Ab is expected and these subjects may be enrolled.

Hepatitis C:

All subjects will be tested for the presence of Hepatitis C Virus antibodies (HCV Ab) at Screening. Samples positive for HCV Ab require PCR qualitative testing for HCV RNA. Any HCV RNA PCR result that meets or exceeds detection sensitivity will be exclusionary. Subjects with a history of treated HCV infection may be allowed to enroll if documentation of effective treatment is available and no evidence of HCV is detected by HCV RNA PCR.

TBNK Assessment By Immunophenotyping

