AST or ALT	
 • Discontinue study drug if confirmed ALT or AST $> 3 \times$ ULN by repeat testing with new sample and either total bilirubin $> 2 \times$ ULN or international normalized ratio > 1.5 
 ○ INR will only be measured in subjects with ALT or AST $> 3 \times$ ULN by the central lab by reflex testing and confirmation is not needed for consideration in toxicity management criteria. • Discontinue study drug if confirmed ALT or AST $> 3 \times$ ULN by repeat testing with new sample along with appearance of fatigue, nausea, vomiting, right upper quadrant pain or tenderness, fever, rash, and/or eosinophilia ($> 5\%$). • Discontinue study drug if confirmed ALT or AST $> 8 \times$ ULN by repeat testing with new sample. • Discontinue study drug if confirmed ALT or AST $> 5 \times$ ULN by repeat testing with new sample for more than 2 weeks. 
For all of the above ALT or AST elevation scenarios, complete supplemental hepatic eCRF.

Serum Creatinine	
 • If serum creatinine is $> 1.5 \times$ the baseline value and $> \text{ULN}$, repeat the test for serum creatinine (with subject in an euvolemic state) to confirm the results. If the results of the repeat testing still meet this criterion then interrupt study drug and re-start study drug once serum creatinine returns to $\leq 1.5 \times$ baseline value and $> \text{ULN}$. • If confirmed serum creatinine $\geq 2.0 \text{ mg/dL}$, interrupt study drug and re-start study drug once serum creatinine returns to normal reference range or its baseline value. 
For the above serum creatinine elevation scenarios, complete supplemental renal eCRF.

Creatine Phosphokinase	
 • If any confirmed CPK value $\geq 4 \times \text{ULN}$ (if symptomatic or asymptomatic), complete supplemental CPK eCRF. • If confirmed CPK $\geq 4 \times \text{ULN}$ accompanied by symptoms suggestive of myositis or rhabdomyolysis, interrupt study drug, complete supplemental CPK eCRF, and contact the AbbVie Therapeutic Area Scientific Director who will discuss with the AbbVie Medical Director.

For allowed study drug interruption, the following rules apply:

- For ABT-494/placebo (daily dosing):

- Allow study drug interruption up to ≤ 14 consecutive days for AEs and emergency surgery during Period 1.
- In Period 2 (after Week 16), study drug interruption due to AEs/surgery is allowed ≤ 21 consecutive days.

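### The Japan waiver of HBV-DNA retesting lacks a core-antibody-negative condition, so a vaccinated HBc Ab+/HBs Ab+ subject may have no scheduled HBV-DNA test on treatment

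*Protocol*

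**What the plan says.** The Japan retest rule and its waiver appear three times in the protocol: Table 2 footnote s (Section 5.3.1), Table 4 footnote e, and the Hepatitis B text of Section 5.3.1.1. Each copy has three parts.

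- **Retest.** A Japanese subject positive at Screening for HBs Ab, HBc Ab or both has HBV-DNA PCR again at Weeks 12 and 24.
- **Stop.** If HBV-DNA recurs, study drug is discontinued.
- **Waiver.** Footnote s: "Retesting at Week 12 and Week 24 is not necessary for subjects that have a history of HBV vaccine and are HBs Ab" (positive). Section 5.3.1.1 and Table 4 footnote e differ by one preposition: "Retesting at Week 12 and Week 24 is not necessary with subjects that have a history of HBV vaccine and are HBs Ab" (positive).

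Section 5.3.1.1 also sets the entry rules. For HBs Ag: "A negative result for HBs Ag will be tested (automatic reflex testing) for core antibodies (HBc Ab) and surface antibodies (HBs Ab"). In the HBc Ab-negative branch no PCR is needed, and for a vaccinated subject "a positive test result for HBs Ab is expected and the subject may be enrolled (Figure 2, Scenario B"). In the other branch, "A positive test result for HBc Ab requires HBV DNA PCR testing (automatic reflex testing"), Scenarios C and D. An HBc Ab-positive subject may enroll if HBV-DNA is negative. The Japan rule, with its waiver, is listed beneath this HBc Ab-positive bullet.

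On the size of the Japanese stratum, Section 5.1 says: "Enrollment in Japan will be capped at 10% of subjects (approximately 4 subjects per group").

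**The concern.** The waiver appears meant for subjects whose surface antibody comes from vaccination. Section 5.3.1.1 draws that inference in the HBc Ab-negative branch, but the waiver does not carry the condition over. Its two stated conditions, vaccine history and HBs Ab+, are also met by a vaccinated subject who is HBc Ab+. The retest rule names HBc Ab+ subjects as people to retest, and the entry rule gives them no vaccine exception.

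For that subject the HBV-DNA stopping rule still stands on paper, but after Screening no scheduled test could trigger it, in a study of up to 88 weeks. A site that followed the text literally would omit both tests without a protocol deviation. The documents give no reason for releasing this pattern and no estimate of its risk, and this point asserts none.

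**Working it through.** No figure in the plan is at issue, so the check applies the written rules to every antibody pattern the retest rule covers.

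**Inputs.** The retest, stop and waiver rules are from Table 2 footnote s, Table 4 footnote e and Section 5.3.1.1. The entry PCR rule is from Section 5.3.1.1. The schedule is the HIV/HBV/HCV row of Table 2, which marks Screening, Week 12 and Week 24 only. The Japan cap is from Section 5.1.

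**Patterns.** All subjects considered are HBs Ag-negative and HBV-DNA-negative at Screening, and so enrollable. There are 3 serologies (HBs Ab+ only, HBc Ab+ only, both) × 2 vaccine states = 6 patterns. These are logical patterns, not patient counts.

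| HBc Ab | HBs Ab | HBV vaccine history | Entry PCR under Section 5.3.1.1 | Weeks 12 and 24 as written | Weeks 12 and 24 with the fix |
|---|---|---|---|---|---|
| − | + | yes | no (Scenario B) | waived | waived |
| − | + | no | no | retest | retest |
| + | − | yes | yes | retest | retest |
| + | − | no | yes | retest | retest |
| + | + | no | yes | retest | retest |
| + | + | yes | yes | **waived** | **retest** |

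**Reading the table.**

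- The waiver releases 2 of 6 patterns. The first row fits Scenario B; the last does not.
- Four patterns are HBc Ab+. Three keep both retests, and 4 − 3 = 1 loses them.
- In that pattern the scheduled HBV-DNA tests would be 1 (Screening) + 2 (Weeks 12 and 24) = 3 without the waiver. With it they are 3 − 2 = 1, with none on treatment.
- With an HBc Ab-negative condition the waiver releases 1 of 6 patterns, and the other five rows do not change.

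**Exclusion criterion 10.** For Japan this criterion applies the PCR test to HBs Ab+ subjects as well, so it covers 6 of 6 patterns at entry. It therefore cannot separate the two waived rows, and the contrast rests on Section 5.3.1.1 alone.

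**Ceiling on numbers.** 10% of 160 = 16 Japanese subjects, or 16 / 4 = 4 per group. The documents do not say how many would be vaccinated and positive for both antibodies.

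**The case against.** The strongest reply is that the three copies agree with each other, and that an entry rule is being used to judge a separate monitoring rule. Outside Japan every HBc Ab+ subject has PCR at entry and nobody has a scheduled retest, so in this protocol entry PCR does not imply retesting. That is correct, and it limits the point to whether the Japan rule does what it states. Within Japan, though, the retest rule itself names HBc Ab+ subjects.

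A second reply is that the waiver could be read as removing only the HBs Ab trigger, leaving HBc Ab+ subjects under the retest sentence. That may well be the intent, but no copy says so. It is true that the wording permits omission and does not forbid testing, which is why the conclusion is that such a subject *may* go untested.

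Third, the supporting text is not airtight. Figure 2, which sets out the four scenarios, is not shown in the text reviewed. Its footnote repeats the vaccination statement without an HBc Ab condition, although the matching asterisk in the text follows the Scenario B sentence. The placement of the Japan rule under the HBc Ab-positive bullet could be deliberate or only layout. If deliberate, it makes an unwritten HBc Ab-negative limit harder for a site to infer.

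Fourth, there are backstops:

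- Chemistry is scheduled at study visits, and Table 6 has liver stopping rules ("Discontinue study drug if confirmed ALT or AST" exceeds the listed limits).
- Section 6.1.7 requires prompt diagnostic testing for a new infection.
- Clinically significant laboratory abnormalities are worked up under local standards.
- The data monitoring committee reviews unblinded safety data.
- Investigators may test at their discretion, and a positive HBV-DNA result found that way would also meet the stopping rule.

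These reduce the consequence, but none is a scheduled HBV-DNA test.

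Finally, the affected group may be empty. That stands, and it sets the severity.

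**Conclusion.** The concern holds as a minor point. As written, all three copies of the waiver release a vaccinated HBc Ab+/HBs Ab+ Japanese subject from both on-treatment HBV-DNA tests. The protocol requires PCR for that subject at entry and otherwise names the subject for retesting. For each such subject the scheduled tests drop from three to one.

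At most about 16 of 160 subjects are in the stratum, and the number with this pattern is unknown and possibly zero. Efficacy, sample size and interpretation are unaffected. The conclusion assumes that sites apply the waiver literally and that Figure 2 adds no HBc Ab condition to it; nothing in the text suggests that it does. No reactivation rate is claimed.

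**What to change.** Add *and are HBc Ab-negative* to the waiver in Table 2 footnote s, Table 4 footnote e and the Hepatitis B text of Section 5.3.1.1, so that it matches the Scenario B branch.

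No new screening data are needed. HBs Ag-negative subjects already have both antibodies measured, and Table 2 footnote f already asks sites to record vaccination: "Also note herpes zoster and hepatitis B vaccination status in medical history". The running cost is two PCRs per affected subject, at Week 12 and Week 24 visits where blood is already drawn. The absolute ceiling is 2 × 16 = 32 PCRs, reached only if every Japanese subject had this pattern. The administrative cost is one clause in three places and, under Section 9.1, ethics committee approval of the amendment before it takes effect; the clause could be included in another amendment.

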5.3.1.1 Study Procedures

The study procedures outlined in [Table 2](#) are discussed in detail in this section, with the exception of exploratory research and validation studies (discussed in [Section 5.3.1.2](#)), drug concentration measurements (discussed in [Section 5.3.2](#)), the collection of prior and concomitant medication information (discussed in [Section 5.2.3](#)), and the collection of AE information (discussed in [Section 6.1.1](#)). All study data will be recorded in source documents and on the appropriate eCRFs.

Informed Consent

At the Screening visit, the subject will sign and date a study specific, IEC/IRB approved, informed consent form before any study procedures are performed or any medications are withheld from the subject in order to participate in this study. Separate written consent will be required for each subject in order to participate in the optional exploratory research and validation studies. Details regarding how informed consent will be obtained and documented are provided in [Section 9.3](#).

Inclusion/Exclusion Criteria

Subjects will be evaluated to ensure they meet all inclusion criteria and have none of the exclusion criteria at both Screening and Baseline Visits.

Medical and Surgical History

A complete non-AD medical and surgical history, including history of alcohol and nicotine use, will be taken from each subject at the Screening visit.

Additionally, a list of each subject's specific AD related medical and surgical history should be recorded at Screening. History of clinical herpes zoster, herpes zoster vaccination, and hepatitis B vaccination status will be recorded as part of the medical history. An updated medical history will be obtained prior to study drug administration at Baseline/Day 1, to ensure the subject is still eligible for enrollment.

A detailed medical history with respect to TB risk factors will be documented in the study source documentation. This information will include BCG vaccination, cohabitation with individuals who have had TB, and travel to, residence in, or work in TB endemic locations.

Atopic Dermatitis Investigator Evaluations

Body Surface Area (BSA)

A qualified investigator should select the subject's right or left hand as the measuring device. For purposes of clinical estimation, the total surface of the palm plus five digits will be assumed to be approximately equivalent to 1%. Measurement of the total area of involvement by the physician is aided by imagining if scattered plaques were moved so that they were next to each other and then estimating the total area involved. The site should make every attempt to have the same qualified Investigator or designee perform all BSA assessments on a given subject throughout the study and are to be performed as specified in [Table 2](#).

Eczema Area and Severity Index (EASI)

A qualified investigator will perform the EASI assessment ([Appendix E](#)). The site should make every attempt to have the same qualified Investigator or designee perform all EASI assessments on a given subject throughout the study, following the schedule in [Table 2](#).

Investigator's Global Assessment for Atopic Dermatitis (IGA)

A qualified investigator will perform the IGA assessment ([Appendix D](#)). The site should make every attempt to have the same qualified Investigator or designee perform all IGA assessments on a given subject throughout the study and are to be performed as specified in [Table 2](#).

SCORing Atopic Dermatitis (SCORAD)

A qualified investigator will perform the SCORAD assessment ([Appendix F](#)). The site should make every attempt to have the same qualified Investigator or designee perform all

SCORAD assessments on a given subject throughout the study and are to be performed as specified in [Table 2](#); via an electronic tablet device provided to sites.

Patient Questionnaires

Subjects will complete the following questionnaires as specified in [Table 2](#):

- Dermatology Life Quality Index (DLQI) ([Appendix G](#))
- Daily Pruritus (itch) Numerical Rating Scale (NRS) ([Appendix H](#))
- Medical Outcomes Study (MOS) Sleep Scale ([Appendix I](#))
- Patient Oriented Eczema Measure (POEM) ([Appendix J](#))
- Asthma Symptoms Questionnaire (only for subjects with asthma symptoms) ([Appendix K](#))
- Daytime Nasal Symptoms Questionnaire (only for subjects with rhinitis symptoms) ([Appendix L](#))
- Atopic Dermatitis Symptom Scale (ADerm-SS) ([Appendix M](#))
- Atopic Dermatitis Impact Scale (ADerm-IS) ([Appendix N](#))
- Patient Global Impression of Severity (PGIS) ([Appendix O](#))

All patient-reported outcomes (PROs) are collected electronically (discussed in [Section 10.2](#)).

The subject should complete the questionnaires before site personnel perform any clinical assessments and before any interaction with clinical site personnel has occurred to avoid biasing the subject's response; except for the questionnaires on the electronic hand-held device (daily Pruritus NRS, ██████████ ADerm-SS and ADerm-IS).

Hand-held device usage stops at the Week 40 visit. Starting at the Week 52 visit, the questionnaires on the hand-held device (Pruritus NRS, ADerm-SS and ADerm-IS) will be given on the tablet during site visits. The MOS Sleep Scale questionnaire will stop at the Week 40 visit. The PGIS, POEM and DLQI questionnaires will be given on the tablet throughout the study as specified in [Table 2](#).

Asthma Symptoms and Daytime Nasal Symptoms questionnaires are collected only for subjects with symptoms of asthma or rhinitis, respectively, at Screening and stop at the Week 40 visit.

TB Testing

The TB screening tests are diagnostic test results to be interpreted in the context of the subject's epidemiology, history, exam findings, etc., and it is the responsibility of the Investigator to determine if a subject has previous, active, or latent TB.

All subjects will be assessed for evidence of increased risk for TB by a risk assessment form ([Appendix C](#)) and tested for TB infection by QuantiFERON-TB Gold Test. The PPD Skin Test should be utilized only when a QuantiFERON-TB Gold Test is not possible for any reason (unless both tests are required per local guidelines). The site staff will complete the TB risk assessment form and enter the data into an appropriate eCRF.

- Preferred Method: QuantiFERON-TB Gold Test will be analyzed by the central laboratory (QuantiFERON test is preferred over PPD skin test).
- If QuantiFERON-TB Gold Test is NOT possible (or if both an Interferon-Gamma Release Assays [IGRA] and PPD Skin Test are required per local guidelines): the PPD Skin Test (also known as a TB Skin Test) will be performed according to standard clinical practice. The TB Skin Test should be read by a licensed healthcare professional between 48 and 72 hours after administration. A subject who does not return within 72 hours will need to be rescheduled for another skin test. The reaction will be measured in millimeters (mm) of induration and induration ≥ 5 mm for AD subjects is considered a positive reaction. The absence of induration will be recorded as "0 mm" not "negative." Subjects who have had an ulcerating reaction to the TB Skin Test in the past should not be re-exposed and should not be tested by a PPD skin test.

If a subject had a negative QuantiFERON-TB Gold (or PPD) test (or IGRA equivalent such as T-SPOT TB test) within 90 days prior to Screening and source documentation is available, the test does not need to be repeated, provided nothing has changed in the

subject's medical history to warrant a repeat test. These cases must be brought to the attention of the AbbVie Therapeutic Area Scientific Director who will discuss with the AbbVie Medical Director and provide a recommendation. The results of the TB test(s) will be retained at the site as the original source documentation.

In the event both a PPD test and a QuantiFERON-TB Gold test are performed, the result of the QuantiFERON-TB Gold test will supersede the result of the PPD test, unless otherwise required by local guidelines. If the QuantiFERON-TB Gold test is indeterminate, the site should repeat the test with another blood sample. If the second QuantiFERON-TB Gold test is also indeterminate, the subject is considered to be positive.

Subjects with a negative QuantiFERON[®]-TB Gold test (OR negative PPD TB skin test) and chest x-ray (CXR) not suggestive of active TB or prior TB exposure may be enrolled. Any positive TB screen after the subject has started the study, should be reported as an adverse event of latent TB (in the absence of an adverse event of active TB).

If the subject has evidence of a latent TB infection (QuantiFERON[®]-TB Gold test or the PPD test positive and the subject has a CXR not suggestive of active TB), prophylactic treatment must be initiated at least 2 weeks prior to administration of study drug (or per local guidelines, whichever is longer). The prophylaxis needs to be completed; however, the full course of prophylaxis does not need to be completed prior to the first dose of study drug. If the Investigator deems that it is necessary, consultation with a TB expert could be considered.

Of note: Rifampicin is not allowed for TB prophylaxis.

Subjects with a prior history of latent TB that have documented completion of a full course of anti-TB therapy within 1 year prior to first study drug administration will be allowed to enter the study provided nothing has changed in the subject's medical history to warrant repeat treatment.

Subjects with a documented completion of a full course of anti-TB therapy greater than 1 year prior to first study drug administration may be allowed to enter the study only after

consultation with the AbbVie Therapeutic Area Scientific Director who will discuss with the AbbVie Medical Director and provide a recommendation.

Newly initiated prophylactic treatment should be captured on the concomitant medications page in the eCRF and in the source documents. Prior therapy should be captured in the eCRF.

Chest X-Ray (CXR)

A CXR (posterior-anterior and lateral views) is required for all subjects at Screening to rule out the presence of TB or other clinically relevant findings. The CXR will not be required if the subject had a previous normal CXR (posterior-anterior and lateral views) within 90 days of Screening, provided all source documentation is available at the site as outlined below and provided nothing has changed in the subject's medical history to warrant a repeat test.

Subjects can have a repeat CXR at any time during the study as warranted, based on the opinion of the Investigator.

Only qualified personnel must perform an assessment of the CXR. The Principal Investigator will indicate the clinical significance of any findings and will sign and date the report. In the assessment of the CXR, the Principal Investigator or their delegate must indicate the presence or absence of (1) calcified granulomas, (2) pleural scarring/thickening, and (3) signs of active TB. If the CXR demonstrates changes suggestive of previous TB (e.g., calcified nodule, fibrotic scar, apical or basilar pleural thickening) or other findings that are clinically significant, the Investigator must contact the AbbVie Therapeutic Area Scientific Director who will discuss with the AbbVie Medical Director before enrolling the subject.

12-Lead ECG

A resting 12-lead ECG will be performed at the designated study visits as specified in [Table 2](#). A qualified physician will interpret the clinical significance of any abnormal

finding, sign, and date each ECG. ECG with QT interval corrected for heart rate using Friedericia's correction formula (QTcF) should be reported (or calculated) and documented in the source documents and later transcribed on to the appropriate eCRF if QTcF prolongation is observed. In these cases, the baseline QTcF will need to be entered into the appropriate eCRF for comparison as well. In addition, any clinically significant findings will be documented in the source documents and later transcribed on to the appropriate eCRF. Each signed original ECG will be monitored by the responsible site monitor and kept with subject's source documents onsite.

For subjects with a normal ECG taken within 90 days of Screening, a repeat ECG at Screening will not be required, provided source documentation is available. If there are other findings that are clinically significant, the Investigator must bring this to the attention of the AbbVie Therapeutic Area Scientific Director who will discuss with the AbbVie Medical Director and provide a recommendation before the subject can be enrolled.

Subjects can have a repeat ECG at any time during the study as warranted, based on the opinion of the Investigator.

Height and Weight

Height will be measured at the Screening Visit only (with shoes off). Body weight will be measured at all scheduled visits, as specified in [Table 2](#). All measurements will be recorded in metric units where applicable.

Vital Signs

Vital sign determinations of systolic and diastolic blood pressure in sitting position, pulse rate (counted for at least 30 seconds after 5 minutes in sitting position), respiratory rate, and body temperature will be obtained at visits specified in [Table 2](#). Blood pressure, pulse rate, body temperature, and respiratory rate should be measured before blood draws are performed.

Physical Examination

A complete physical examination will be performed at the designated study visits as specified in [Table 2](#). The physical examination at the Baseline Visit will serve as the baseline physical examination for the entire study. Physical examination abnormalities noted by the Investigator at Baseline prior to the first dose of study drug will be recorded in the subject's medical history; abnormalities noted after the first dose of study drug will be evaluated and documented by the Investigator as to whether or not the abnormality is an AE (see Section [6.1.1](#) for AE definition). All findings, whether related to an AE or part of each subject's medical history, will be captured on the appropriate eCRF page.

At any time, a symptom-directed physical examination can be performed as deemed necessary by the Investigator.

Pregnancy Test

A serum pregnancy test will be performed for all female subjects of child bearing potential at the Screening Visit and the Week 88 or PD visit. The serum pregnancy test will be sent to and performed by the central laboratory. If the serum pregnancy test is positive the subject is considered a screen failure. If the serum pregnancy test is indeterminate, it should be repeated ≥ 3 days later to determine eligibility. If the repeat serum pregnancy test is:

- Positive, the subject is considered a screen failure;
- Negative, the subject can be enrolled into the trial;
- Still borderline ≥ 3 days later, this will be considered documentation of continued lack of a positive result and the subject can be enrolled into the study in the absence of clinical suspicion of pregnancy and other pathological causes of borderline results.

A urine pregnancy test will be performed for all female subjects of childbearing potential at the Baseline Visit prior to the first dose of study drug and at all subsequent visits. More

frequent pregnancy tests will be performed throughout the study if required per local/country requirements.

- If the baseline urine pregnancy test performed at the site is negative, then dosing with study drug may begin. If the baseline urine pregnancy test performed at the site is positive, dosing with study drug must be withheld and a serum pregnancy test is required. The serum pregnancy test will be sent to and performed by the central laboratory. If the serum pregnancy test is positive, study drug must be withheld and the subject must be discontinued from the study. In the event a pregnancy test comes back borderline, a repeat test is required.
- If a urine pregnancy test post baseline is positive, study drug needs to be temporarily discontinued and a serum pregnancy test is required. The serum pregnancy test will be sent to and performed by the central laboratory. If the serum pregnancy test is positive, study drug must be permanently discontinued.

In Period 2, for women of childbearing potential, a urine pregnancy test will be performed at all visits and monthly at home between scheduled study visits (at Weeks 28 and 36 at home, unless an on-site visit is necessary due to rescue therapy with topical corticosteroids per Section 5.2.3.4). The results of the monthly at home tests will be communicated to the site. If a urine pregnancy test is positive, the subject must stop dosing, come in to the clinic and have blood drawn for a serum pregnancy test that will be analyzed at the central laboratory.

At each visit, the study staff should review the pregnancy avoidance recommendations with each subject of childbearing potential and male subjects with a partner of childbearing potential, and document this discussion in the subject's source records.

A pregnant or breastfeeding female will not be eligible for participation or continuation in this study.

Clinical Laboratory Tests

Blood and urine samples will be obtained for clinical laboratory tests listed in [Table 4](#). Samples will be obtained at the designated study visits in [Table 2](#).

Unscheduled clinical labs may be obtained at any time during the study if deemed appropriate per Investigator's discretion. A certified central laboratory will be utilized to process and provide results for the clinical laboratory tests. All abnormal laboratory tests that are considered clinically significant by the investigator will be followed to a satisfactory resolution.

The central laboratory chosen for this study will provide instructions regarding the collection, processing, and shipping of these samples.

Blood draws should be performed after all clinical assessments and questionnaires and vital sign determinations have been completed; but before any study drug administration during a visit.

For clinic visits where samples for serum chemistry and/or advanced lipid panel tests are collected, subjects should be fasting (a minimum 8-hour fast) whenever possible. If a subject is not able to fast when necessary, due to unforeseen circumstances, the non-fasting status will be recorded in study source documentation.

Urine samples will be obtained for urinalysis testing at visits specified in [Table 2](#). The central laboratory will be responsible for performing a macroscopic urinalysis (urine dipstick) on the collected urine specimens. Specified abnormal macroscopic urinalyses defined as leukocytes, nitrite, protein, ketones, or blood greater than negative, or glucose greater than normal will be followed up with a microscopic analysis at the central laboratory.

For any laboratory test value outside the reference range that the investigator considers to be clinically significant the Investigator should apply the standard of care for medical

evaluation and treatment per local guidelines (see Section 6.1.7 for toxicity management guidelines):

- The investigator will repeat the test to verify the out-of-range value.
- The investigator will follow the out-of-range value to a satisfactory clinical resolution.

A laboratory test value that requires a subject to be discontinued from the study drug or requires a subject to receive treatment will be recorded as an AE. The central laboratory chosen for this study will provide instructions regarding the collection, processing and shipping of these samples. The baseline laboratory test results for clinical assessment for a particular test will be defined as the last measurement prior to the initial dose of study drug.

Table 4. Clinical Laboratory Tests

Hematology	Clinical Chemistry ^a	Urinalysis ^b	Other Laboratory Tests
Hematocrit	Blood Urea Nitrogen (BUN)	Specific gravity	Central Lab Tests:
Hemoglobin	Creatinine	Ketones	Serum Pregnancy (bHCG)
RBC count	Total bilirubin	pH	test ^d
WBC count	INR (reflex only) ^c	Protein	HBsAg ^e
Neutrophils	Albumin	Blood	HBsAb ^e
Bands	Aspartate aminotransferase	Glucose	HBcAb ^e
Lymphocytes	(AST)	Urobilinogen	HBV DNA PCR reflex only ^e
Monocytes	Alanine aminotransferase	Bilirubin	HCV Ab ^e
Basophils	(ALT)	Leukocytes	HCV RNA reflex only ^e
